5.2 Missing values

Primary endpoint In patients with missing information on micro- or macrobleeds at baseline, any lesion detected on follow-up T2*- or SWI MRI will be considered as new lesion (section 4.1 and sensitivity analysis 3). For missing values in the primary endpoint (e.g. due to missing follow-up), inverse probability of censoring weights will be estimated. Thereby stabilized inverse probability of weights for missingness of the primary endpoint will be estimated for each treatment arm according to (Robins et al., 2000) and (Hernan & Robins, 2006; Austin & Stuart, 2015). The weights will be estimated on the PP except for the sensitivity analysis 2, where the FAS will be used. The following variables will be used to estimate the weights: age, sex, occlusion of dissected artery, and National Institutes of Health Stroke Scale (NIHSS). If the patient did not have a stroke, 0 will be imputed for the NIHSS. Missing values will be further investigated in sensitivity analyses (see sensitivity analysis 1).

Covariates Missing values in covariates used to estimate the inverse probability of censoring weights will be imputed. If the number of missing values does not exceed 5% in each variable of interest the median (continuous variables) or the mode (= most frequent category, categorical variables) will be used. If there is one covariate with more than 5% missing values, 5 multiple imputations will be done as described in van Buuren & Groothuis-Oudshoorn (2011). To this end we will generate 5 imputed data sets. In a second step we will estimate the weights for each imputed data set. Thereafter, we will stabilize and average the weights over the 5 imputations. In case of severe variability of the stabilized weights between imputations, we will increase number of imputations. Thereby the weights will be considered to have "severe variability between imputations" if for any patient the inter-weight variability divided by the number of imputations (the amount the variance would be increased in order to correct for the uncertainty of the imputations when using Rubin's rule, Barnard & Rubin (1999)) is larger than 0.01.

Secondary endpoints: The number of missing values will be presented. No imputations will be performed. Secondary analyses will be complete case analyses.

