4.1 Primary endpoint

The primary endpoint - **Cerebrovascular Ischemia**, major **Hemorrhagic events** or **Death (CIHD)** - is a composite endpoint. It is defined as the occurrence of at least one of the following events during the treatment period:

1. Cerebral ischemic events (clinical) or surrogate findings for cerebral ischemia:
 - (a) Any ischemic stroke, defined as: new symptomatic neurologic deterioration lasting at least 24 hours that was not attributable to a non-ischemic cause, or a new symptomatic neurologic deterioration that was not attributable to a non-ischemic cause and was accompanied by neuroimaging evidence of a new brain infarction. ([Amarenco et al. \(2018\)](#)). This includes Transient Ischemic Attack (TIA) with Diffusion Weighted Imaging (DWI) lesion. Ischemic stroke also includes retinal infarction defined according to ([Hayreh & Zimmerman \(2005\)](#))
 - (b) New acute ischemic lesions on DWI MRI since baseline are defined as: (1) those with an unequivocal lack of continuity between new and existing (on baseline imaging) lesions on the same slice as well as on adjacent slices – irrespective of vascular territories and lesion pattern, ([Gensicke et al. \(2015\)](#)) and (2) “acute” being defined as a hyperintense signal alteration on DWI with a corresponding hypointense or isointense signal on ADC (Apparent Diffusion Coefficient) maps ([Gensicke et al. \(2015\)](#)).
2. Hemorrhages (clinical) or surrogate findings:
 - (a) any major extracranial hemorrhage: any clinically apparent extracranial bleeding requiring any kind of intervention [including hospitalization or prolongation of hospitalization] or leading to death.
 - (b) any symptomatic intracranial hemorrhage defined as: any documented intracranial hemorrhage - i.e. an acute extravasation of blood into the brain parenchyma ([Amarenco et al. \(2018\)](#)) - that was temporally related to any deterioration in the patient’s clinical condition.
 - (c) any new, asymptomatic micro- or macrobleeds (visible on follow-up brain T2*-MRI or Susceptibility weighted imaging (SWI), which were absent on the baseline MR-scan) defined as: (1) those with an unequivocal lack of continuity between new and existing (on baseline imaging) lesions on the same slice as well as on adjacent slices – irrespective of vascular territories and lesion pattern, ([Gensicke et al. \(2015\)](#)) and lesions being defined as hypointense brain lesions with clear margins on T2*-MRI or SWI.

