4.3 Model and method of analysis

The difference in CIHD rate $\pi_{\text{anti-coagulant treatment}} - \pi_{\text{anti-platelet treatment}}$ will be compared with the non-inferiority margin using a two-sided 95 % confidence interval. We will use Wilson's method to calculate CI (continuity-corrected modification of the Wilson's score method [Newcombe, 1998](#)). The primary analysis will be performed on the PP. Section 5.2 describes the handling of missing values.

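### Section 5.2 weights a single missing/observed indicator for the composite, although a clinical event is known without an MRI and a non-event is not

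*SAP*

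**What the plan says.** SAP Section 4.1 defines the primary endpoint (CIHD) as a composite: "It is defined as the occurrence of at least one of the following events during the treatment period". Some components are clinical: stroke, symptomatic intracranial haemorrhage, death and major extracranial haemorrhage, the last described as "any clinically apparent extracranial bleeding requiring any kind of intervention". Others can be seen only on a follow-up scan: new DWI lesions, and new asymptomatic bleeds on T2* or SWI.

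Section 4.3 states: "The primary analysis will be performed on the PP". It sends missing values to Section 5.2, which says: "For missing values in the primary endpoint (e.g. due to missing follow-up), inverse probability of censoring weights will be estimated". There, "stabilized inverse probability of weights for missingness of the primary endpoint will be estimated for each treatment arm", with age, sex, occlusion of the dissected artery and NIHSS as predictors.

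The SAP does not say when the composite counts as missing. In particular, it does not classify a patient with a clinical event and no follow-up MRI, or a patient with neither. The per-protocol criteria in Section 2 exclude a visit-1 MRI outside its time window but are silent on one that was not done.

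**The concern.** The composite is positive as soon as one component is positive, and negative only when all are known to be negative. A stroke, major bleed or death therefore settles it without a scan. A patient who stays well and misses the scan has an undetermined composite. If such patients are treated as missing, the probability of being observed is 1 after a clinical event and below 1 otherwise.

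Inverse probability weighting on four covariates assumes that, given those covariates, being observed is unrelated to the outcome. Here the endpoint's own construction breaks that assumption within every covariate stratum, so a better-fitting weight model does not help. What is at stake is the accuracy of each arm's rate in the primary analysis and, if the arms are unbalanced, of the risk difference that is compared with the margin.

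**Working it through.** The SAP gives no event rate, sample size or missing-MRI rate, so there is no planned figure to reproduce. The only document input is the margin of 0.12 (Section 4.2). The other inputs are assumptions, shown as ranges:

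- c, clinical-event risk: 2% to 10%
- s, risk of an imaging event among patients free of a clinical event: 10% to 20%
- m, share without a follow-up MRI: 5% to 20%

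**Per-arm bias.** The true rate is c + (1−c)s. The rate among patients whose composite is known is [c + (1−c)s(1−m)] / [c + (1−c)(1−m)]. Subtracting gives

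bias = c(1−c)m(1−s) / [c + (1−c)(1−m)],

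which is above zero whenever 0 < c < 1, m > 0 and s < 1. The same holds within any covariate stratum.

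Example with c = 0.05, s = 0.15, m = 0.10:

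- True rate: 0.05 + 0.95×0.15 = 0.1925.
- Observed rate: (0.05 + 0.95×0.15×0.90) / (0.05 + 0.95×0.90) = 0.17825/0.905 = 0.1970.
- Bias: 0.0045.

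Over the assumed ranges the bias runs from 0.0008 (c = 0.02, s = 0.20, m = 0.05) to 0.0198 (c = 0.10, s = 0.10, m = 0.20).

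**Does the planned weighting remove it?** One arm was simulated with 2,000,000 patients per scenario and a logistic weight model on the four named covariates:

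| c, m (approx.) | True | Unweighted | Planned weights | Weights as in the fix |
|---|---|---|---|---|
| 2%, 10% | 0.173 | 0.174 | 0.175 | 0.173 |
| 5%, 10% | 0.199 | 0.203 | 0.204 | 0.199 |
| 5%, 20% | 0.199 | 0.208 | 0.210 | 0.199 |
| 8%, 20% | 0.225 | 0.240 | 0.241 | 0.225 |

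The planned weights did not reduce the bias.

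**Bias in the difference, antiplatelet minus anticoagulant** (s = 0.15 in both arms):

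| c, antiplatelet / anticoagulant | m, antiplatelet / anticoagulant | True | Estimated | Bias |
|---|---|---|---|---|
| 0.05 / 0.05 | 0.10 / 0.10 | 0 | 0 | 0 |
| 0.08 / 0.02 | 0.10 / 0.10 | 0.051 | 0.056 | +0.005 |
| 0.08 / 0.02 | 0.20 / 0.20 | 0.051 | 0.062 | +0.011 |
| 0.05 / 0.05 | 0.05 / 0.15 | 0 | −0.005 | −0.005 |
| 0.10 / 0.10 | 0.05 / 0.20 | 0 | −0.015 | −0.015 |

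A positive bias works against non-inferiority and a negative one favours it. Within the assumed ranges the difference cannot be off by more than 0.0198 − 0.0008 = 0.0190. That needs every rate at its most unfavourable end, in opposite directions in the two arms.

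**Planned sensitivity analyses.** Take c = 0.05, s = 0.15, m = 0.10 in both arms.

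- Analysis 1a (missing = event) gives 0.05 + 0.95×(0.135 + 0.10) = 0.27325 in each arm, so a difference of 0.
- Analysis 1b (missing = non-event) gives 0.05 + 0.95×0.135 = 0.17825 in each arm, again a difference of 0.
- Crossing them, event for antiplatelet and non-event for anticoagulant, gives 0.27325 − 0.17825 = 0.095.

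Imputing the same value in both arms therefore does not bound the difference.

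**The case against.** The strongest reply is that the premise is not written down. Section 5.2 offers only missing follow-up as an example, and the SAP never says that a patient with no MRI and no clinical event is missing. That is right, and the point is conditional on that reading. The alternatives do not rescue the text:

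- Scoring such patients as non-events understates each rate by (1−c)·s·m, for example 0.95×0.15×0.10 = 0.014.
- Calling the composite missing even after a known stroke or death discards known events, and analysis 1b would then recode them as non-events.
- Treating a missed MRI as a per-protocol deviation would remove these patients rather than weight them, but Section 2 does not say so.

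For patients who withdraw consent, only baseline data enter the full analysis set, so the mechanism does not operate for them there.

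Second, the plan already probes missing data. Analyses 1a/1b and 2a/2b keep known clinical events and bracket each arm's rate. Analysis 7 uses clinical components only and is untouched by a missed MRI. This stands as mitigation, not as correction: the imputations use the same value in both arms, 2c reuses the same weights, and 7 answers a different question.

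Third, a reader might infer that the primary risk difference is necessarily biased, or that a non-inferiority conclusion would be unsafe. The document does not support either. The bias is assured only in each arm's rate and cancels in the difference when the arms are alike. An 8% versus 2% clinical risk has no basis in the SAP.

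**Conclusion.** The defect is real but moderate. If clinical-event-free patients without MRI are the missing ones, the Section 5.2 weights leave each arm's CIHD rate biased upward by about 0.1 to 2 points. This rests on assumed rates of c 2–10%, s 10–20% and m 5–20%.

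The effect on the difference ranges from none, when all three rates match across arms, to about 1.5 points in either direction in the scenarios examined. It is conservative when the antiplatelet arm has more clinical events or missed MRIs, and favours non-inferiority when the anticoagulant arm does. Against a 12-point margin it could decide the result only if the confidence limit falls close to the margin. The rule should still be corrected, because it governs the primary estimate, the missing category is undefined, and no planned analysis repairs it.

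**What to change.** In Section 5.2:

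1. State that a patient with a known clinical event is an observed event regardless of MRI, and that a clinical-event-free patient without an evaluable follow-up MRI is missing.
2. Estimate MRI-availability weights by arm among clinical-event-free followed patients only. Give clinical-event patients an MRI weight of 1.
3. Use a separate weight for complete loss to clinical follow-up, which the MRI weight does not address.
4. Leave the MRI weights unstabilized, or stabilize them only in a way that preserves the ratio of event to event-free patients. With m constant at 0.10, a weight of 1/0.90 in the event-free group returns 0.1925, the true rate in the example. A stabilized weight of 0.90/0.90 = 1 returns 0.1970 and brings the whole bias back.
5. Add an arm-differential (crossed or tipping-point) version of sensitivity analysis 1.

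Item 2 removes the bias only if, among clinical-event-free patients, MRI absence is random given the covariates. Item 5 tests that assumption.

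This defect does not require replacing the planned interval with a bootstrap. The cost is SAP wording, slightly more programming and somewhat more variable weights; no new data are needed.

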4. **Effect of failure to preserve the randomization due to major protocol deviations:**⁴ We will use stabilized inverse probability weights to assess the impact of patients excluded from the PP analysis set according to (Robins et al., 2000) and (Hernan & Robins, 2006; Austin & Stuart, 2015). The weights will be estimated on the FAS. Thereby we will use the following variables: age, sex, occlusion of dissected artery and National Institutes of Health Stroke Scale (NIHSS). If the patient did not have a stroke, 0 will be imputed for the NIHSS. Thereafter the main analysis will be repeated including the weights. By doing so, patients without deviation who are similar to the patients with deviation will be inflated (compared to and patients without similarities).
5. **Assessing a modelling approach:** we compare the probability of CIHD between trial arms using a logistic regression model. The incidence of CHID will be the dependent variable. Treatment will be used as independent factor. In addition, the model will include the presence of cerebral ischemic events clinically and/or neuroradiologically (i.e., clinically defined ischemic stroke, or DWI-lesions at baseline, or both) and occlusion of the dissected artery as covariates to adjust for baseline differences among patients.
6. **Effect of minor protocol deviation:**⁵ The main analysis will be repeated excluding patients who were randomized or initiated treatment more than 72h after initial MRI scan, which was considered to be a minor protocol deviation.

⁴This sensitivity analysis was not planned in the protocol. However we think it helps to further assess the potential bias introduced when randomized patients are excluded from the analysis set due to major protocol deviations.

⁵This sensitivity analysis is a consequence of the adaption in section 2 ("major" vs. "minor" protocol deviations).

7. **Effect of imaging endpoint (as compared to clinical endpoints):**⁶ The main analysis will be repeated including only the clinical endpoints ICH, stroke, extracranial hemorrhage and death as components of the primary endpoint.

All patients with a primary or secondary outcome event will be listed by the PI. For the primary outcome events, the PI will provide information on type, timepoint of the outcome event and relation to the allocated treatment (antiplatelets vs anticoagulants). Laboratory values quantifying coagulation at the time of the event will be provided if available.

5 Secondary objective

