5.1 Secondary endpoints

1. new ischemic strokes (including retinal infarction)
2. new acute lesions on diffusion-weighted MRI
3. any major extracranial hemorrhage
4. any symptomatic intracranial hemorrhage
5. any asymptomatic micro- or macro-bleeds
6. any death
7. any increase in volume of the vessel wall hematoma on follow-up cervical MRI as compared to the baseline MR-scan.
8. modified Rankin scale at 3 and 6 months
9. independence in activity of daily living (i.e. modified Rankin scale 0-2) at 3 months and at 6 months
10. excellent functional outcome (i.e. modified Rankin scale 0 or 1) at 3 and 6 months
11. any TIA (classical definition)
12. recurrent cervical artery dissection

All secondary endpoints will be presented descriptively. The particular events leading to the primary endpoint (1 – 6) will be summarized as frequencies and percentages. If patients died while under observation (endpoint 6), we will provide the number of patients with cerebrovascular death. Patients with more than one event will be listed. Time between treatment initiation and event will be presented. The summaries will be done on the PP as well as on the FAS.

⁶This sensitivity analysis is planned since the significance of DWI lesions is still debatable. It also allows to compare the results with studies assessing only clinical endpoints.

The effect of treatment (anti-platelet vs. anti-coagulation) on mRS at three months (endpoint 8) will be assessed in a proportional odds model (also called ordinal logistic regression or shift-model). "Independence in activity" and "excellent functional outcome" at three months (endpoints 9 and 10) will be modelled in logistic regression models. Presence of cerebral ischemic events clinically and/or neuradiologically (i.e., clinically defined ischemic stroke, or DWI-lesions at baseline, or both), occlusion of the dissection arteries and mRS before dissection will be included as covariates to adjust for baseline differences among patients. The models will be fit on the PP.

The analyses of other endpoints, described as tertiary endpoints in the study protocol, will be described elsewhere. This also includes the interaction tests of antiplatelet versus anti-coagulant treatment and MMP9/TIMP2 ratio or other biomarker signatures.

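### The weight models in SAP 5.2 and 4.5 item 4 see baseline ischemia only through NIHSS, so DWI-only lesions and strokes scoring 0 are weighted as no ischemia

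*SAP*

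**What the plan says.** The SAP uses inverse probability weights for two purposes.

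- **Missing primary endpoint (section 5.2).** These censoring weights enter the main analysis, because section 4.3 refers to 5.2 for missing values. The predictors are fixed: "The following variables will be used to estimate the weights: age, sex, occlusion of dissected artery, and National Institutes of Health Stroke Scale (NIHSS"). The weights "will be estimated for each treatment arm". They are fitted on the PP, or on the FAS for sensitivity analysis 2.
- **Exclusion from the PP (section 4.5, item 4).** These weights serve one sensitivity analysis and are fitted on the FAS. The list is the same: "age, sex, occlusion of dissected artery and National Institutes of Health Stroke Scale (NIHSS").

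For both, the score is filled in for patients without stroke: "If the patient did not have a stroke, 0 will be imputed for the NIHSS".

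The outcome regressions use a different variable. In item 5 of section 4.5, the logistic model for the primary endpoint, "the model will include the presence of cerebral ischemic events clinically and/or neuroradiologically", defined as "clinically defined ischemic stroke, or DWI-lesions at baseline, or both". Occlusion of the dissected artery is the other covariate. In section 5.1 the models for endpoints 8 to 10 take the same ischemia variable, occlusion and the mRS before dissection, which "will be included as covariates to adjust for baseline differences among patients".

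**The concern.** Weights correct selection only on what is in the weight model. Of the two baseline covariates in item 5, occlusion is carried into the weights and the ischemia indicator is not. NIHSS stands in for it only in part, because three groups share the value 0:

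1. no ischemia;
2. a DWI lesion without clinical stroke;
3. a clinical stroke scoring 0.

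What is lost is largely the imaging part of baseline ischemia. New DWI lesions are a component of the primary endpoint (section 4.1, 1(b)), so baseline DWI status is a plausible predictor of outcome.

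The two weight models carry different stakes. In 5.2, selection among NIHSS-0 patients with and without ischemia would leave a residual in the primary estimate itself. In item 4, which is meant to show whether PP exclusions introduce bias, selection on a variable absent from the model cannot show up.

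**Working it through.** The SAP states no event rate, missingness rate, exclusion rate or sample size for this point, so there is no figure to reproduce. The check compares the variable lists and then illustrates the size.

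**Lists side by side**

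| Analysis | Stroke, NIHSS > 0 | Ischemia with NIHSS 0 | Occlusion |
|---|---|---|---|
| 5.2 censoring weights | yes, via NIHSS | no | yes |
| Item 4 exclusion weights | yes, via NIHSS | no | yes |
| Item 5 logistic model | yes, via indicator | yes | yes |
| mRS models (5.1) | yes, via indicator | yes | yes |

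**Illustration.** Every rate here is an assumption.

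- Strata: no ischemia (share *a*), ischemia with NIHSS 0 (share *d*), stroke with NIHSS > 0 (share 0.50), so *a* = 0.50 − *d*. *d* runs from 5 % to 30 %.
- Event risk: 10 % without ischemia; 20 % to 40 % with it.
- Missingness in one arm: 5 % without and 20 % with ischemia, or 10 % and 40 %. In the other arm it is 10 % in every stratum, so that arm is unbiased.
- NIHSS is simplified to 0 versus above 0; age, sex and occlusion are ignored.

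Formulas for the affected arm, with stratum share *s*, risk *r* and missingness *m*:

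- True rate = Σ *s r*.
- Complete-case rate = Σ *s*(1 − *m*)*r* / Σ *s*(1 − *m*).
- NIHSS-weighted rate = 0.50 × (observed rate among NIHSS 0) + 0.50 × (observed rate among NIHSS > 0).
- With the indicator added, each stratum is restored to its share and the true rate is recovered.

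Largest case (*d* = 0.30, risk 10 % vs 40 %, missing 10 % vs 40 %):

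- True: 0.20 × 0.10 + 0.80 × 0.40 = 0.340.
- Observed shares: 0.20 × 0.9 = 0.18; 0.30 × 0.6 = 0.18; 0.50 × 0.6 = 0.30; total 0.66.
- Complete case: (0.018 + 0.072 + 0.120)/0.66 = 0.318, off by 2.18 points.
- NIHSS-weighted: 0.50 × (0.018 + 0.072)/0.36 + 0.50 × 0.40 = 0.125 + 0.200 = 0.325, off by 1.50 points.

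Smallest case (*d* = 0.05, risk 10 % vs 20 %, missing 5 % vs 20 %):

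- True: 0.45 × 0.10 + 0.55 × 0.20 = 0.155.
- NIHSS-weighted: 0.50 × (0.04275 + 0.008)/0.4675 + 0.50 × 0.20 = 0.1543, off by 0.07 points.

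Selected results, as absolute bias in the risk difference in percentage points:

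| *d* | Risk with ischemia | Missing without / with ischemia | Overall missing in that arm | Complete case | NIHSS-weighted | Indicator added |
|---|---|---|---|---|---|---|
| 5 % | 20 % | 5 % / 20 % | 13 % | 0.43 | 0.07 | 0.00 |
| 5 % | 40 % | 10 % / 40 % | 27 % | 3.03 | 0.47 | 0.00 |
| 10 % | 30 % | 10 % / 40 % | 28 % | 2.00 | 0.57 | 0.00 |
| 20 % | 30 % | 10 % / 40 % | 31 % | 1.83 | 0.92 | 0.00 |
| 30 % | 20 % | 5 % / 20 % | 17 % | 0.29 | 0.21 | 0.00 |
| 30 % | 40 % | 10 % / 40 % | 34 % | 2.18 | 1.50 | 0.00 |

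Overall missing is *a* × *m* without ischemia plus (1 − *a*) × *m* with it; in the last row, 0.20 × 0.10 + 0.80 × 0.40 = 0.34. Across all scenarios NIHSS-based weights removed about 28 % to 85 % of the complete-case bias, least when many patients have ischemia with NIHSS 0. The affected arm's rate comes out too low, so the sign of the error in the comparison depends on which arm it is. The same arithmetic applies to item 4 with exclusion in place of missingness.

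**The case against.** **NIHSS already does much of the work.** A reader might infer that baseline ischemia is absent from the weights and that selection on it goes wholly uncorrected. The SAP does not support that: a score above 0 marks a clinical stroke and also grades it, which a yes/no indicator does not. This objection stands and limits the point to ischemia at NIHSS 0.

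**The SAP does not rank the covariates.** It is tempting to say that the weights omit the variable the SAP regards as most prognostic. Item 5 and section 5.1 list ischemia beside occlusion, only to adjust for baseline differences.

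**Missingness and exclusion are separate mechanisms.** Discontinued treatment and missed visit windows are PP exclusions (section 2). The 5.2 weights model a missing endpoint and do not address exclusions in the main PP analysis, so a larger 5.2 model would not correct them. This also stands.

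**Other planned analyses help.** Item 5 adjusts for the very indicator. If its model is correct and selection depends only on arm and its covariates, its conditional odds ratio is protected. But the SAP states no conversion to the risk difference that is tested against the margin. Items 1, 2(a) and 2(b) impute all events or no events by the same rule in both arms, so they do not fully bound selection that differs by arm. Item 2(c) reuses the 5.2 variables.

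**Outcome and missingness models need not share covariates.** True, and the lists do not contradict each other. The indicator also overlaps NIHSS, and arm-specific models with few missing outcomes have little room for another parameter. This is why the point is an improvement and not an error.

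**Conclusion.** The point holds as a minor one. Both weight models treat patients with DWI-only lesions or strokes scoring 0 as having no ischemia, while the SAP's own regressions distinguish them, and no reason is given.

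The arm comparison is biased only if these patients differ in event risk and their missingness or exclusion differs by arm, or if the treatment effect varies with ischemia. Similar selection in both arms would largely cancel. Under the assumed rates the residual after NIHSS-based weighting is about 0.1 to 1.5 points, against the 12-point margin of section 4.2. The upper end needs 34 % missing in one arm and 30 % of patients with ischemia at NIHSS 0. The actual size is unknown, and nothing in the SAP suggests that the non-inferiority conclusion would turn on it.

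**What to change.** - **Section 4.5, item 4:** add the item 5 indicator (clinical stroke or DWI lesion at baseline, yes/no) to the variables for the exclusion weights.
- **Section 5.2:** add the same indicator to the censoring-weight models where the number of missing outcomes allows, with the condition fixed in advance. Otherwise state why NIHSS alone is considered enough.
- **Both:** keep age, sex, occlusion and NIHSS.

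The cost is one added variable in two lists, from data already needed for item 5. The downside is one more parameter, which may be unstable in the arm-specific 5.2 models if few outcomes are missing.

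### The complete-case rule removes patients with a known 3-month mRS from the adjusted models when one baseline covariate is missing, so these explorative comparisons can lose precision (minor)

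*SAP*

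**What the plan says.** For secondary endpoints, SAP section 5.2 says: "The number of missing values will be presented. No imputations will be performed". It then adds: "Secondary analyses will be complete case analyses".

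Section 5.1 specifies three adjusted comparisons of function at three months. The mRS itself "will be assessed in a proportional odds model", and the two dichotomies (mRS 0-2 and mRS 0-1) "will be modelled in logistic regression models". All three are fitted on the per-protocol set. They include baseline ischemia (clinical, on DWI, or both), and in addition "occlusion of the dissection arteries and mRS before dissection will be included as covariates to adjust for baseline differences among patients".

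Section 5.2 treats another set of covariates differently: "Missing values in covariates used to estimate the inverse probability of censoring weights will be imputed". That set is "age, sex, occlusion of dissected artery, and National Institutes of Health Stroke Scale (NIHSS"). The method begins: "If the number of missing values does not exceed 5% in each variable of interest the median (continuous variables) or the mode". If any covariate exceeds 5%, the plan makes five imputed data sets, estimates the weights in each, and averages the weights.

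Sensitivity analysis 5 in section 4.5 is a logistic model for the primary endpoint with baseline ischemia and occlusion as covariates. Section 4.5 refers its missing values to section 5.2.

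**The concern.** Deleting a patient because a baseline value is missing discards an outcome that was observed. For the mRS models the SAP orders this without giving a reason, although for the weights it provides a way to keep such patients. Occlusion shows the difference most clearly: one missing value is filled in for the primary analysis and removes the same patient from all three mRS models.

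Two further effects follow. The adjusted models may rest on fewer patients than the descriptive mRS tables. And in sensitivity analysis 5 the plan does not say what happens to a patient with missing baseline ischemia, because that variable is not in the weight model and so falls outside the imputation rule.

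At stake is the precision of the only modelled comparisons of function in the SAP, and a small gap in one supportive analysis of the primary endpoint.

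**Working it through.** **Which rule reaches which covariate**

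| Covariate | In the weight model, so imputed there | In mRS models (endpoints 8-10) | In sensitivity analysis 5 |
|---|---|---|---|
| Occlusion | yes | yes, complete case | yes |
| Baseline ischemia | no | yes, complete case | yes, no rule |
| Pre-dissection mRS | no | yes, complete case | not used |
| Age, sex, NIHSS | yes | not used | not used |

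Only occlusion is shared between the weight model and the mRS models.

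**Patients dropped.** The SAP states no sample size, power or missing rate for these models, so there is no figure to reproduce. Assumption: each of the three covariates is missing completely at random in a share *m* of patients.

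- Full overlap of the gaps: share dropped = *m*
- Independent gaps: share dropped = 1 - (1 - *m*)³
- No overlap: share dropped = 3*m*
- Rise in standard error ≈ 1/√(1 - share dropped) - 1

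For *m* = 5% and independent gaps, 1 - 0.95³ = 0.143 and 1/√0.857 = 1.080, a rise of 8.0%.

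| *m* per covariate | Dropped, independent (range) | Rise in SE, independent (range) |
|---|---|---|
| 0% | 0% | 0% |
| 1% | 3.0% (1.0-3.0%) | 1.5% (0.5-1.5%) |
| 2% | 5.9% (2.0-6.0%) | 3.1% (1.0-3.1%) |
| 5% | 14.3% (5.0-15.0%) | 8.0% (2.6-8.5%) |
| 10% | 27.1% (10.0-30.0%) | 17.1% (5.4-19.5%) |

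The 5% row is the SAP's own switching threshold, used here as a reference point and not as a forecast.

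**Does imputation recover the loss?** Simulated logistic model with 200 patients, 1500 runs, no treatment effect, three binary covariates with assumed prevalences 0.6, 0.3 and 0.1, and independent gaps. Standard deviation of the treatment log odds ratio:

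| *m* | Full data | Complete case | Mode imputation | Complete case / mode |
|---|---|---|---|---|
| 1% | 0.307 | 0.312 | 0.307 | 1.016 |
| 2% | 0.316 | 0.328 | 0.315 | 1.041 |
| 5% | 0.311 | 0.336 | 0.308 | 1.091 |

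Simulations with 85 per arm and a true odds ratio of 2 (both assumed) gave the same picture: complete case about 3-4% worse at 2% missing and 8-10% worse at 5%.

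**Does imputation cost anything?** With arms balanced at baseline, the mean log odds ratio after mode imputation was 0.71-0.72, against 0.71-0.72 on full data (true value 0.69). With a deliberately large imbalance (ischemia 70% against 50%, occlusion 45% against 25%), large samples gave 0.66 at 5% missing and 0.62 at 10% under mode imputation. Complete case gave 0.70 at both. The largest shift is thus 0.69 - 0.62 = 0.07. At 85 per arm with that imbalance, coverage stayed near 95%, and mode imputation had the lower mean squared error.

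**The case against.** **It is a stated rule in an explorative analysis.** Section 5.1 calls all secondary analyses hypothesis-generating and rejects a significant/non-significant reading. This stands: the point concerns efficiency, and a loss of power is not the right measure of it. But explorative status is no reason to discard observed outcomes.

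**The rule may be meant for missing outcomes only.** The paragraph is headed by the endpoints. Its last sentence, however, governs analyses. On the narrower reading the mRS models would have no covariate rule at all, and the same sentence would still be needed.

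**Missing covariates may be rare.** Section 5.2 falls back on the centers' evaluations when images cannot be provided for central control. A clinical stroke settles baseline ischemia without DWI. Occlusion and DWI lesions are both imaging findings, so their gaps may overlap. This stands, and it points to the low end of the table.

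**Imputation is not free.** The models use the per-protocol set, analyzed by treatment received, so balance at baseline is not assured, and simple imputation weakens the adjustment. This stands, but the effect was small even under a large assumed imbalance.

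**Stronger readings that the SAP does not support.** A reader might infer that precision is certainly lost; without missing rates that cannot be said. A reader might infer that the SAP imputes these very covariates elsewhere; that is true of occlusion alone. A reader might infer that the existing covariate rule can simply be extended; above 5% it averages weights and does not say how to pool a treatment estimate.

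**Conclusion.** The point holds as a minor one. The complete-case rule excludes patients with an observed 3-month mRS from the adjusted models for endpoints 8 to 10 when baseline ischemia, occlusion or pre-dissection mRS is missing. Occlusion is handled differently for the primary-analysis weights without a stated reason, and baseline ischemia in sensitivity analysis 5 has no rule.

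The size depends on missing rates that the SAP does not give. There is no loss if nothing is missing. With independent gaps (assumed), the standard error rises about 3-4% at 2% missing per covariate and about 8-10% at 5%. If the gaps overlap fully, the rise is 1.0% and 2.6%.

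A reader might infer that the non-inferiority conclusion is at risk. It is not: the primary analysis in section 4.3 is an unadjusted difference in rates with its own missing-data rule, and none of the models discussed here enters it.

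**What to change.** In section 5.2:

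- Limit the complete-case rule to patients whose secondary outcome is missing.
- For the models of endpoints 8 to 10 and for sensitivity analysis 5, impute missing baseline covariates by median or mode if no covariate exceeds 5% missing.
- If any covariate exceeds 5%, use multiple imputation, fit the model in each imputed data set, and pool the treatment estimates and their standard errors by Rubin's rules. Averaging weights does not apply here.
- Report the number of patients with imputed covariates in each model, and show the complete-case result alongside.

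Cost: a few sentences in the SAP, a little more analysis work, and no new data. The small downside is that median or mode imputation slightly weakens the covariate adjustment if the per-protocol arms differ at baseline; the complete-case result shown alongside makes this visible. If no covariate is missing, no result changes.
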